3.4.3. Intent-to-Treat-c (ITT-c)

The Intent-to-Treat (ITT-c) Population includes all subjects in the SAF Population with their SARS-CoV-2 status confirmed by central RT-PCR viral load at baseline \geq lower limit of quantification (LLOQ) and with at least one post-baseline primary efficacy measurement. Subjects will be analyzed as randomized.

The reasons for exclusion from the ITT-c population will be summarized by treatment group using the Safety population.

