5.3. Baseline Disease Characteristics

The following baseline disease characteristics will be presented by treatment group and overall and stratified by age group and duration of baseline COVID-19 symptoms (≤ 3 days or > 3 days and ≤ 5 days) for all subjects in the SAF, ITT-c and PP populations. Additionally, baseline disease characteristics will be listed for all subjects in the SAF population.

- SARS-CoV-2 RNA viral load
- Infectious SARS-CoV-2 viral load
- SARS-CoV-2 RNAemia
- SARS-CoV-2 serostatus
- Respiratory pathogen test
- SARS-CoV-2 variant
- COVID-19 symptom diary total score

- COVID-19 symptom diary severity

SARS-CoV-2 RNA viral load, Infectious SARS-CoV-2 viral load and SARS-CoV-2 RNAemia will also be summarized as positive, negative and missing where either a numeric or “POS” result is considered positive and TND is considered negative.

Baseline SARS-CoV-2 serostatus will be based on Day 1 SARS-CoV-2 anti-nucleocapsid and anti-spike IgG, and IgM antibodies. If at least one qualitative result is positive or IgM > 1.0, the serostatus will be considered positive. In order to be considered negative, all four results must be non-missing, all qualitative results must be negative and IgM equal to “<1.0”.

A description of how symptoms are scored from the COVID-19 Symptom Diary is in [Appendix 14.2](#). The total symptom score and the following severity categories will be presented:

- Only mild symptoms at Day 1
- 1 moderate and no severe symptoms
- 2 or more moderate symptoms and no severe symptoms
- 1 or more severe symptom(s) and no moderate symptoms
- 1 or more severe symptom(s) and 1 or more moderate symptom(s)

6. Treatments and Medications

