7.4. Electrocardiogram

All Electrocardiogram (ECG) results will be summarized by treatment group and visit in the Safety population and a listing will be presented of all results with abnormalities flagged.

8. Efficacy Analysis

Unless otherwise specified, efficacy analyses will be performed using ITT-c population and the following methods will be implemented:

For time to event endpoints time and date will be used and 24 hours will be considered as a day. Descriptive statistics using the Kaplan-Meier method will include the median, 25th percentile, and 95% CIs (log-negative-log transformation). Additionally, the cumulative event rate (SE) will be summarized by treatment group and presented graphically over time. For between group comparisons, Cox Proportional Hazards models (tie handling will be addressed first using the exact method then with Efron's method if the exact method does not converge) will include treatment group, randomization stratification factors of age (≤ 50 years or 51 to 64 years) and duration of COVID-19 symptoms (≤ 3 days or >3 days and ≤ 5 days), and the baseline value of the endpoint. The hazard ratios with associated 95% CIs (Wald) and p-values (analysis of maximum likelihood estimates) comparing EDP 235 [REDACTED] versus Placebo, and EDP 235 [REDACTED] versus Placebo will be reported. Model assumptions will be checked via a log-negative-log plot and/or Schoenfeld residuals as appropriate. Subjects who do not achieve the specified endpoint will be censored with time imputed as treatment start time as follows:

COVID-19 diary:

- Subjects who have not been followed through the Day 33 visit (discontinuation from study or incomplete follow-up at the time of analysis) or completed Day 33 diary will be censored at Day 33.

Other time to event endpoints:

- Subjects who discontinued from the study will be censored at Day 33.
- Subjects who have completed the Day 33 visit will be censored at Day 33 Visit Date.

For treatment comparisons of change from baseline endpoints, analysis of covariance (ANCOVA) models will include treatment group, randomization stratification factors of age (≤ 50 years or 51 to 64 years) and duration of COVID-19 symptoms (≤ 3 days or >3 days and ≤ 5 days) and baseline value of the endpoint as the covariate. The least-squares means, SE, and 95% CIs will be presented for individual groups and the difference between groups. The p-value for

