8.2.7. Change from Baseline in SARS-CoV-2 RNA Viral Load Assessed by RT-qPCR Through Day 33

The antiviral activity of EDP 235 on viral kinetics will be measured using SARS-CoV-2 RNA viral load assessed by RT-qPCR of NP swab samples on Days 1, 3, 5, 9, 14, and 33. Change from baseline values for SARS-CoV-2 RNA viral load will be summarized using the methods described in [Section 8](#).

8.2.8. Change from Baseline in Infectious SARS-CoV-2 Viral Load Assessed by Cell Culture Infectivity Assay Through Day 33

The infectious SARS-CoV-2 viral load will be measured using a SARS-CoV-2 cell culture infectivity assay of NP swab samples on Days 1, 3, 5, 9, 14 and 33. Change from baseline values for infectious SARS-CoV-2 viral load will be summarized using the methods described in [Section 8](#).

8.2.9. AUC of SARS-CoV-2 RNA Viral Load Assessed by RT-qPCR Through Day 33

The area under the curves (AUC) from Day 1 through Day 33 will be calculated for SARS-CoV-2 viral load data using actual sampling times via non-compartmental analysis using Phoenix[®] WinNonlin[®] Version 8.3.4 or higher according to the linear trapezoidal with linear interpolation

8.3.4. AUC of SARS-CoV-2 RNAemia Viral Load Through Day 33

The area under the curve (AUC) from Day 1 through Day 33 will be calculated for SARS-CoV-2 RNAemia viral load data using actual sampling times via non-compartmental analysis using Phoenix® WinNonlin® Version 8.3.4 or higher according to the linear trapezoidal with linear interpolation. AUCs will be derived for Days 1-14 and Days 1-33. Additionally, the AUC from Day 1 through Day 14 and the AUC from Day 1 through Day 33 will be standardized for 14 and 33 days by multiplying $14, 33/t_{last}$ where t_{last} is the actual time in days of the last available assessment. No AUC values will be calculated if there are less than 3 results available. The same methods used in [Section 8.2.9](#) will be applied.

8.3.5. Time to SARS-CoV-2 RNAemia TND Through Day 33

Time to SARS-CoV-2 RNAemia to TND is defined as per [Section 8.1.1.2](#) and will be summarized and analyzed as described in [Section 8](#).

8.3.6. Change from Baseline in SARS-CoV-2 Nucleocapsid Antigenemia Through Day 33

Change from baseline of SARS-CoV-2 nucleocapsid antigenemia will be summarized as described in [Section 8](#).

8.3.7. Proportion of Subjects with Positive SARS-CoV-2 Serostatus at Day 33

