 - If the day and month are missing or a date is completely missing, it will be considered as missing.

Imputation rules for SARS-CoV-2 viral load and SARS-CoV-2 nucleocapsid antigenemia data:

- SARS-CoV-2 RNA and RNAemia viral load values reported as TND will be imputed with 1 copy/mL (i.e., 0 log₁₀ copies/mL)
- Infectious SARS-CoV-2 viral load values reported as TND will be imputed with 1 TCID₅₀/mL (ie, 0 log₁₀ TCID₅₀/mL).
- SARS-CoV-2 nucleocapsid antigenemia reported as TND will be imputed as 1 fg/mL.
- Numeric values <LLOQ will be set to the LLOQ.
- Numeric values >ULOQ will be set to the ULOQ.
- Values reported as “POS” will be imputed as half of the LLOQ.
- Imputed values will be used in tables and listings will present actual data.

Imputation rules for PK concentrations

- Serum concentrations that are <LLOQ will be treated as zero for PK analyses, except for <LLOQ values observed between 2 quantifiable concentrations and <LLOQ values that occur after the first quantifiable point, which will be set to missing. If consecutive <LLOQ concentrations are followed by quantifiable concentrations in the terminal phase, those concentrations after <LLOQ concentrations will be treated as missing. Missing concentrations will be treated as missing in the PK parameter calculations.

Imputation rules for all other data:

- No other imputations will occur for any data not previously mentioned.

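### SAP 8.2.8 analyses change in infectious viral load only in all ITT-c subjects, so those culture-negative at baseline, already at the floor of the scale, dilute the estimated antiviral effect

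*SAP*

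**What the plan says.** - **Endpoint.** SAP 8.2.8 states "Change from baseline values for infectious SARS-CoV-2 viral load will be summarized using the methods described in" and then points to the general methods of Section 8. The cultures come from NP swabs taken at six visits between Day 1 and Day 33. It names no subset.
- **Population.** The opening of Section 8 says that, unless otherwise specified, "efficacy analyses will be performed using ITT-c population".
- **Entry to that population.** Section 3.4.3 takes treated subjects "with their SARS-CoV-2 status confirmed by central RT-PCR viral load at baseline" at or above the LLOQ. That is an RNA criterion; culture status plays no part.
- **Value given to a negative culture.** Appendix 14.5: "Infectious SARS-CoV-2 viral load values reported as TND will be imputed with" 1 TCID50/mL, which is 0 log10.
- **Negative cultures at baseline are provided for.** Section 5.3: "Infectious SARS-CoV-2 viral load and SARS-CoV-2 RNAemia will also be summarized as positive, negative and missing", with TND counted as negative. This table is by treatment group and covers ITT-c.
- **Methods.** Section 8 plans an ANCOVA with treatment, the two stratification factors and the baseline value. It adds a pooled two-sample t-test on change and line graphs of both adjusted and unadjusted means.

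**The concern.** For RNA, the ITT-c definition ensures that every analysed subject starts with a quantifiable amount of virus to clear. The culture endpoint sits beside it under the same viral-load objective but has no matching condition. A subject with quantifiable RNA and a negative culture enters at 0 log10, and any change can only be zero or upward.

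Pooling these subjects with culture-positive ones averages a group that can show a fall with a group that cannot. ANCOVA with one common slope and one treatment coefficient does not undo this averaging: the treatment term is still a mean over both groups. The unadjusted t-test and mean plots have a further problem, because the gap between the two groups' mean changes enters the variance. A chance imbalance in the culture-negative share then shifts the raw difference directly.

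At stake is the reading of antiviral activity in a Phase 2 trial with two active arms. A real reduction in infectious virus could look small because many subjects had none to lose. The primary safety objective is not affected.

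**Working it through.** **Plan's own figure.** There is none to reproduce. The SAP shown gives no sample size, power, SD or effect for this endpoint. From the SAP come 1:1 allocation for each dose against placebo, two-sided alpha 0.05, the 0 log10 floor and the two methods. Everything else below is assumed.

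**Step 1: dilution.** Let f be the culture-negative share at baseline and D the mean difference among baseline-positives. With no late conversion, the all-ITT-c difference is (1 - f) × D. For D = -0.55:
- f = 0.2: 0.8 × -0.55 = -0.44
- f = 0.4: 0.6 × -0.55 = -0.33
- f = 0.6: 0.4 × -0.55 = -0.22

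**Step 2: unadjusted test, by formula.** Let d be the size of the effect in positives, s the SD of their change and m their mean fall. All subjects: effect (1 - f)d, variance (1 - f)s² + f(1 - f)m², n per arm. Positives only: effect d, SD s, n(1 - f) per arm. Take n = 75, d = 0.5, s = 1.0.
- f = 0.2, m = 1: effect 0.40, variance 0.80 + 0.16 = 0.96. Power is 0.705 in all subjects against 0.782 in 60 positives per arm.
- f = 0.4, m = 2: effect 0.30, variance 0.60 + 0.96 = 1.56. Power is 0.312 against 0.660 in 45 per arm.

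Over f = 0.2 to 0.6 and m = 1 to 2 the loss runs from about 8 to 35 points.

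**Step 3: simulation without late conversion.** Assumed: 75 per arm, baseline mean 3 log10 (SD 1.0) in positives, placebo fall 1.5, extra drug fall 0.7, residual SD 1.0, floor 0, 2,000 runs. Strata are omitted from the model.

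| Culture-negative | Estimate, all / positives | ANCOVA power, all / positives | t-test power, all / positives |
|---|---|---|---|
| 20% | -0.44 / about -0.55 | 0.91 / 0.93 | 0.73 / 0.92 |
| 40% | -0.33 / about -0.55 | 0.80 / 0.84 | 0.46 / 0.83 |
| 60% | -0.22 / about -0.55 | 0.63 / 0.69 | 0.28 / 0.67 |

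The t-test loses 19, 37 and 39 points. ANCOVA loses 2, 4 and 6 points as tabulated; the simulation error of each power is about 1 point (for example √(0.65 × 0.35 / 2,000) = 0.011), so the last figure is compatible with 5.

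**Step 4: other settings.** Assumed: baseline mean 2.5 (SD 1.2), residual SD 1.0, effect 0.5 or 0.7 before flooring, placebo fall 1.0 or 2.0, and late conversion of 5% of negatives on placebo and 2.5% on drug. With effect 0.5 and fall 1.0, the estimate is -0.32, -0.25 and -0.17 at 20%, 40% and 60% negative, against -0.40 in positives. ANCOVA power is 0.69 vs 0.70, 0.57 vs 0.58 and 0.43 vs 0.41; t-test power is 0.58 vs 0.69, 0.40 vs 0.56 and 0.26 vs 0.40. Over all these settings, restriction changes ANCOVA power by about -3 to +4 points and raises t-test power by about 10 to 30.

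**Step 5: more late conversion, ANCOVA.** Step 3 setting, late-positive mean assumed 2 log10; power in all subjects vs positives at 20%, 40% and 60% negative:
- 10% convert in both arms: 0.86 vs 0.94, 0.68 vs 0.85, 0.39 vs 0.67
- 10% placebo, 5% drug: 0.91 vs 0.94, 0.79 vs 0.86, 0.62 vs 0.68
- 10% placebo, 3% drug: 0.92 vs 0.94, 0.84 vs 0.85, 0.75 vs 0.69

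**The case against.** The all-ITT-c comparison is a legitimate randomized average over confirmed, treated subjects. The dilution runs toward the null, does not inflate type I error, and concerns a secondary endpoint with no multiplicity control. All of this stands. A reader might infer that the planned analysis is invalid or must be replaced; the SAP does not support that.

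A reader might also infer a serious power loss in the adjusted model. Steps 3 and 4 do not show one, because the baseline covariate absorbs most of the added heterogeneity. Nor are culture-negative subjects uninformative. Subjects enter within 5 days of onset, so a culture may turn positive later, and preventing that would be a drug effect. Step 5 shows the ANCOVA comparison changing sign on this unknown input.

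It would be too strong to say that the pooled estimate reflects case mix instead of the drug. It reflects both, and so does the restricted one: a simulated drug effect of 0.70 is estimated at about 0.55 even in positives, because some of them reach the floor as well.

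Section 5.3 shows that negative baselines are foreseen but not how many fall within ITT-c, since the same sentence serves three assays and three populations. It does already provide the culture-negative count by arm, so a reader could gauge the dilution. That is no omission.

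Parts of the text from 8.2.9 into 8.3 are not shown, and a further culture analysis could sit there. Section 8.2.8 is complete as printed and points to none. The subgroup list in 8.1.3 covers only the primary efficacy endpoints and does not include culture status.

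**Conclusion.** The concern holds as a matter of estimation. As written, 8.2.8 yields only a mean difference scaled down roughly by the culture-positive share, which is about 20%, 40% or 60% smaller when that share of subjects is culture-negative. Baseline adjustment does not restore it. The unadjusted t-test also loses roughly 10 to 40 power points across the simulated settings. Under ANCOVA the loss is about 0 to 5 points without late conversion; with conversion it can be larger, or reverse if the drug prevents it.

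These sizes rest on assumed sample size, viral levels, SD, effect and culture-negative share; if few ITT-c subjects are culture-negative, the problem is small. That a negative baseline cannot fall also assumes that half the assay's LLOQ, the value given to unquantified positives, is not below 1 TCID50/mL; the SAP does not state this LLOQ. The change is worth making but is not critical to the trial.

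**What to change.** In Section 8.2.8, before unblinding, add the ANCOVA and the unadjusted comparison in ITT-c subjects whose baseline infectious viral load is positive by the Section 5.3 flag. Name this as the analysis used to read the size of the antiviral effect. Keep the all-ITT-c analysis and report the two side by side, including in the mean plots.

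The cost is SAP wording and one more set of outputs. The flag is already derived and no new data are needed. Because the subset is defined by baseline status, the randomized comparison is preserved; fixing it now avoids a choice that would look post hoc. The drawbacks are fewer subjects in that model and an estimate still partly limited by the floor. The culture-negative count by arm need not be requested again.

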3.1. Incomplete and Missing Data

Imputation rules for missing dates of prior/concomitant medications, including COVID-19 vaccinations and prohibited medications, and procedures are provided in [Appendix 14.5](#).

Imputation rules for missing AE data are provided in [Appendix 14.5](#).

Data that are continuous in nature but are reported in the form $<x$, $>x$, $\leq x$, or $\geq x$ (where x is considered as the limit of quantitation) will be set to limit of quantitation value with the following exceptions:

- Efficacy endpoint data will be imputed as detailed in [Appendix 14.5](#).
- PK concentrations data will be imputed as detailed in [Appendix 14.5](#).

- Other incomplete/missing data will not be imputed, unless specified otherwise.

All analyses will be conducted using SAS Version 9.4 or higher. Unless otherwise stated, a two-sided test will be used at a significance level (alpha) of 0.05 for all analyses. Two-sided 95% confidence intervals (CI) will be provided when appropriate.

Summary Tables and Figures will be presented by treatment group and will be labelled as follows:

- “EDP 235 [REDACTED]”
- “EDP 235 [REDACTED]”
- “Placebo”

All subject data will be presented in individual subject data listings. Dates will be shown in subject listings as they have been recorded. Unless otherwise stated, unscheduled visit results will be included in date/time chronological order, within subject listings only. All listings will be sorted by subject number, date/time and visit. The treatment group (randomized) as well as subject’s sex and age will be stated on each listing. Unless otherwise stated, data listings will be based on all subjects randomized.

When no data are available for a table or listing, an empty page with the title will be produced with suitable text (e.g., “There are no records for this table/listing.”). For analyses where convergence or the analysis cannot be performed, “NC” (not calculable) will be presented in summary tables.

For the reporting of this study both CDISC SDTM (SDTM Implementation Guide version 3.3 or later) and ADaM (ADaM Implementation Guide version 1.3 or later) standards will be applied.

[REDACTED]

[REDACTED]

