4.1. Disposition

A subject will be considered to have completed the study after his/her attendance at the last planned study visit (Day 33 ± 1 day), or the last unscheduled visit (if any occur), as applicable. For each subject his or her study completion status (Yes/No) is recorded on the End of Study CRF.

The number of subjects randomized and in the SAF, ITT-c, PP, PK and IPK populations will be summarized using frequencies and percentages. All percentages will be based on the number of subjects randomized.

Subject disposition will be summarized by treatment group and overall, for all subjects who are randomized. A disposition of subjects includes the number and percentage of subjects for the following categories: subjects who were randomized, subjects who completed study treatment per protocol, subjects who discontinued study treatment early, subjects who completed the study, subjects who discontinued from the study early. All percentages will be based on the number of subjects randomized. The reasons for discontinuation of study treatment and study participation will also be summarized in this table.

The reason for discontinuation of study treatment or study participation may include any of the following:

- Adverse event
- Lost to follow-up
- Pregnancy
- Protocol deviation
- Study terminated by sponsor
- Withdrawal by subject
- Physician decision
- Death
- Other reason

Subject disposition data will also be presented in listings, including a listing by analysis population.

Screen failures were not included in the study database and will not be included in any SDTM or ADaM datasets. If required, a listing of screen failures from all screened subjects, including the inclusion or exclusion criteria that were not met, may be provided from vendor IRT data.

A separate listing of subjects that were randomized, treated and then found to meet exclusion or fail to meet inclusion criteria will be provided including the inclusion or exclusion criteria.

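### Scaling the RNAemia AUC by 14/t_last and 33/t_last overstates profiles that have cleared or fallen substantially by the last sample, and t_last has neither a window nor a time origin

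*SAP*

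**What the plan says.** SAP Section 8.3.4 (AUC of SARS-CoV-2 RNAemia) uses the linear trapezoidal rule on actual sampling times. It states "AUCs will be derived for Days 1-14 and Days 1-33", and then adds a standardized version in which "the AUC from Day 1 through Day 33 will be standardized for 14 and 33 days by multiplying" by 14 or 33 over t_last. One definition of t_last serves both windows: it "is the actual time in days of the last available assessment". The only data requirement visible there is "No AUC values will be calculated if there are less than 3 results available". For the analysis methods the section points to Section 8.2.9, whose text breaks off in the public copy.

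Appendix 14.5 fixes the value of a cleared sample: "SARS-CoV-2 RNA and RNAemia viral load values reported as TND will be imputed with 1 copy/mL", that is, 0 on the log10 scale. Missing later visits are not filled in. Section 3.1 says "Other incomplete/missing data will not be imputed, unless specified otherwise", and Appendix 14.5 closes with "No other imputations will occur for any data not previously mentioned".

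**The concern.** Two separate things are wrong.

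First, multiplying by window length over t_last is an extrapolation. It is sound only if the load after the last sample resembles the average load before it. In an acute infection the expected course is clearance, and the SAP itself analyses time to RNAemia TND in Section 8.3.5. Two subjects with the same clearance can therefore receive different standardized AUCs only because one missed a late visit. In effect the scaling is an imputation of missing visits, in a plan that otherwise rules out imputing them.

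Second, the text does not say whether t_last for the 14-day AUC is the last sample within 14 days or the last sample overall, nor whether it is a study day or elapsed time since Day 1. Two programmers could follow the text and produce different numbers.

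**Working it through.** The plan gives no AUC value to reproduce, so the check applies its rule directly.

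**Inputs.** From the SAP: windows W = 14 and 33, factor W/t_last, linear trapezoids, TND = 0 log10. Assumed: AUC taken on the log10 scale; the load profiles below; samples on Days 1, 3, 5, 9, 14 and 33, which are the nasopharyngeal swab days (no RNAemia sampling days are visible).

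**What the rule does.** AUC × W/t = AUC + (W − t) × AUC/t. If t is elapsed time, AUC/t is exactly the mean observed load, and each unobserved day is credited with it. If t is a study day, AUC/t is slightly below that mean. The scaled value is too high whenever the true mean load over the unobserved days is below AUC/t.

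**Case needing no assumed decline curve.** A subject with some detectable RNAemia is TND at Day 14 and stays TND. The area from Day 14 to Day 33 is 0.
- Attends Day 33: factor 33/33 = 1.00.
- Misses Day 33: factor 33/14 = 2.36.
- With elapsed days in numerator and denominator: 32/13 = 2.46.
- Unscaled AUC: identical in both subjects, and correct.

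**Illustrative profiles** (t_last as study day, tied to the window):

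| log10 load, Days 1/3/5/9/14/33 | Last sample, window | AUC to last sample | Scaled | Complete | Ratio |
|---|---|---|---|---|---|
| 4, 3, 2, 1, 0, 0 | Day 14, W = 33 | 20.5 | 20.5 × 33/14 = 48.3 | 20.5 | 2.36 |
| 6, 5, 4, 2, 1, 0 | Day 14, W = 33 | 39.5 | 39.5 × 33/14 = 93.1 | 49.0 | 1.90 |
| 4, 3.8, 3.6, 3.3, 3, 2 | Day 14, W = 33 | 44.75 | 44.75 × 33/14 = 105.5 | 92.25 | 1.14 |
| 4, 3.8, 3.6, 3.3, 3, 2 | Day 5, W = 14 | 15.2 | 15.2 × 14/5 = 42.6 | 44.75 | 0.95 |
| flat at 2 | Day 14, W = 33 | 26.0 | 26.0 × 33/14 = 61.3 | 64.0 | 0.96 |

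The fourth row fits the condition above: AUC/t = 15.2/5 = 3.04, while the mean load over Days 5–14 is (44.75 − 15.2)/9 = 3.28, which is higher. With elapsed days throughout, the same case gives (15.2/4)/(44.75/13) = 1.10, so the direction for slow decliners depends on the unstated time origin.

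**Window of t_last.** Take the first profile, Day 1–14 AUC = 20.5.
- Completer, t_last read literally as Day 33: 20.5 × 14/33 = 8.7 (factor 0.42).
- Same Day 1–14 samples, no Day 33 sample: 20.5 × 14/14 = 20.5 (factor 1.00).

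**Time origin.** If t_last is elapsed time but the numerators stay at 14 and 33, even a profile complete for its window is inflated, by 14/13 = 1.08 or 33/32 = 1.03.

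**Dependence on the sampling days.** With swab days, three results can exist by Day 5, so the factor can reach 14/5 = 2.80 or 33/5 = 6.60 (elapsed: 13/4 = 3.25, 32/4 = 8.00). On an assumed sparser schedule of Days 1, 5, 14 and 33, three results force t_last to Day 14 or later. The 14-day factor is then 14/14 = 1.0 and the 33-day maximum 33/14 = 2.36.

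**The case against.** The scaled AUC is an addition to the unscaled one. In the clearest case, TND at Day 14 with Day 33 missed, the unscaled value is correct; for other truncated profiles it is a lower bound. Time to RNAemia TND also describes clearance without any scaling. This stands, and it limits the weight of the point, but it does not make the standardized figure right.

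A sensible programmer would probably take t_last as the last sample within the window, because multiplying a complete 14-day AUC by 14/33 defeats the purpose of standardizing to 14 days. That is fair. The text still does not say so, and the literal reading gives a materially different number. The missing part of Section 8.2.9 might define t_last or add a data requirement. It would not remove the proportional scaling, which Section 8.3.4 states outright.

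Three stronger readings are tempting and not supported:
- **Every incomplete declining profile is overstated.** The slowly declining profile above gives 0.95 when t_last is a study day.
- **Inflation of 2.8 to 8.0 should be expected.** Those factors need swab days applied to RNAemia and clearance by Day 5. The SAP shows neither RNAemia sampling days nor RNAemia loads.
- **The treatment comparison is biased.** Nothing is given on missing visits or clearance by arm, so neither the size nor the direction of such a bias can be stated.

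Subjects TND throughout have a log10 AUC of 0 and are unaffected.

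**Conclusion.** The point holds for profiles that have cleared or fallen substantially by the last sample. For a subject cleared by Day 14 who misses Day 33, the overstatement is 2.36-fold (2.46-fold in elapsed days). This rests only on the stated rule, the TND value in Appendix 14.5, the log10 scale and the subject remaining clear. Flat or very slowly declining profiles are about neutral or slightly understated on a study-day basis. The definition of t_last is ambiguous in window and origin; taken literally, it gives 0.42 against 1.00 for identical Day 1–14 data. How many subjects are affected is unknown. Importance is minor to moderate: the error lies in a stated rule, but in an endpoint outside the primary and secondary set, with an unscaled AUC alongside.

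**What to change.** In Section 8.3.4:
- Define t_last as the last assessment within each window, state its time origin, and use elapsed days in both numerator and denominator. A complete profile then has factor 13/13 or 32/32 = 1.
- Do not scale up a profile whose last sample is TND; its remaining area is about 0 provided it stays clear.
- For other profiles without a sample near the window end (for example within the schedule's ±1 day), rely on the unscaled AUC to the last sample and report the number truncated by arm. Do not interpret the scaled 33-day AUC on its own.
- Apply the same rule in Section 8.2.9 if it uses this scaling.

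Cost: a few lines of SAP text and a small programming change. The unscaled AUC remains a lower bound for profiles truncated before clearance: in the second profile of the table it is 39.5/49.0 = 0.81 of the complete value. Multiple imputation of missed visits, or restriction to subjects sampled at the window end, could be added as a sensitivity analysis. The first assumes data missing at random and would need the no-imputation statements in Section 3.1 and Appendix 14.5 amended; the second makes the summary depend on who attended. Neither is required for this endpoint.
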